2.2 Study Objectives

This abbreviated statistical analysis plan incorporates only the following objectives for which analysis datasets and TFL outputs from Veristat are required:

Objectives of Part B	
Primary Objectives	To evaluate the overall response rate (ORR) of the 40/15 regimen based on the IRC assessment of tumour response rates in adult participants with relapsed rituximab/anti-CD20 refractory FL.
Secondary Objectives	To evaluate the overall response rate (ORR) of the 100/20 regimen based on the IRC assessment of tumour response rates in adult participants with relapsed rituximab/anti-CD20 refractory FL. To evaluate the complete response rate (CRR), duration of response (DOR), Duration of complete response (DoCR) and Progression Free

	
Survival (PFS) of the 40/15 and 100/20 regimens based on the IRC assessment of tumour response rates.
 
Safety (Parts B and C)
 
 To characterise the safety profile of Betalutin in terms of Adverse Events and laboratory data.
--	---

2.3 Study Endpoints

Primary Endpoints	Part B: Overall Response Rate (ORR) as assessed by IRC assessment based on standard criteria [Cheson 2014]
Secondary Endpoints	
Efficacy(Part B)
 
 CRR by IRC assessment DoR and DCoR by IRC assessment PFS by IRC assessment 
Safety endpoints (Part B and C):
 
 Incidence and severity of adverse events (AEs). Laboratory data

2.4 Sample Size and Power

As described in the Introduction the study was terminated early and so is not powered to meet the original study objectives. Summaries and listings of the data collected will be provided (as detailed in Tables 1 and 2 in Section 1).

3 General Considerations for Data Analyses

3.1 General

Summary statistics for continuous variables will consist of number of non-missing observations (n), mean, standard deviation, minimum, 25th percentile, median, 75th percentile and maximum, unless specified otherwise. The precision (number of decimal places) of these variables is defined in the tables, figures and listings (TFLs) shells document – minimum and maximum will be presented to the same level of precision as the raw data; mean, median, percentiles will be presented to 1 additional decimal place; standard deviation will be presented to 2 additional decimal places.

For categorical variables the number and percentage of participants in each category will be presented, based on the number of non-missing observations apart from disposition of participants, protocol deviations, background and demographic characteristics, prior and concomitant medications/procedures and adverse events where the percentage will be based on the number of participants in the analysis set.

3.2 Analysis Sets

Assignment of participants to analysis sets will be agreed between the study statistician and the client prior to database lock or data extraction for any final formal run and review of outputs, once all study data are available for the respective run.

3.2.1 Screened Set

The screened set includes all participants who provided informed consent.

3.2.2 Efficacy Analysis set

Efficacy Analysis set will be a subset of the Part B participants who received Betalutin and were assigned either “40/15” or “100/20” dose levels.

3.2.3 Safety Analysis Set

The Safety Analysis Set (SAF) will consist of all participants who received at least one dose of study intervention (rituximab, lilotomab or Betalutin). Participants are reported according to the treatment they actually received.

3.3 Derived Data

- *Definition of study day*

Study day is relative to the date of first administration of Betalutin and lilotomab (study Day 1). Therefore, study day for rituximab will be negative.

Note: in the protocol, Betalutin administration day is referred to as Day 0. However, for statistical analysis and to be in line with CDISC requirement, Betalutin administration day will be defined as Day 1, the day before Day 1 is defined as Day -1 and there is no Day 0.

- *Definition of baseline*

Study baseline is defined as the last non-missing value (including scheduled and unscheduled assessments) prior to rituximab dosing. This will usually be the latest value collected at the screening visit.

Betalutin baseline is defined as the last value measured prior to lilotomab and Betalutin dosing. A visit window from day -2 to day 1 (prior to lilotomab and Betalutin dosing) will be used.

- *Incomplete dates*

For calculation purposes, incomplete dates will generally be completed using worst case. For example, the 15th of the month will be used when day is missing and 1st July when day and month are missing.

Further details are given in the relevant sections as required.

- *Non-numeric values*

In the case where a variable is recorded as “>x”, “≥x”, “<x” or “≤x”, then for analysis purposes a value of x will be taken. Where a range of values is quoted the midpoint of the range will be taken.

- *Month windows*

For the laboratory values and change from baseline outputs, to take account of the potential for out of window assessments being conducted due to the COVID-19 pandemic, the following Month labels will be rederived using the table below.

Table 3: LYMRIT-37-01 study, Part B Month Windows

Month	Days relative to the date of Betalutin administration *
Week 8	Days 53 to 61

Week 12	Days 81 to 89
Month 3	Days 78 to 122
Within the first 3 Months	Days 1 to 122
Within the first 6 Months	Days 1 to 213

* (Date of assessment – date of Betalutin administration) +1 if date of assessment is on or after date of Betalutin administration. Otherwise (Date of assessment – date of Betalutin administration).

3.4 Data Presentation

The TFLs will present the dose regimens (where relevant) as detailed below:

Table 4: LYMRIT-37-01 study, Part B/C Treatment Group Descriptors

Order	Descriptor for Dose Regime (where relevant) to be presented in TFLs	Meaning of Descriptor
1 [1]	40 / 12.5	40 mg lilotomab plus 12.5 MBq/kg Betalutin
2	40 / 15	40 mg lilotomab plus 15 MBq/kg Betalutin
3	100 / 20	100 mg/m ² lilotomab plus 20 MBq/kg Betalutin
4 [1]	Received Rituximab only	Received Rituximab only
5 [1]	Enrolled no treatment	Enrolled but did not receive any trial treatment
6 [1]	Screen failure	Participants in the screened set who failed screening (i.e. are not eligible to join the study per the eligibility eCRF page).

[1] In table summaries, if there is insufficient space to present all treatment groups on a single page, these dose regimens will be presented on the next page.

The data will be summarised in tabular form by Study Part (i.e. B / C) and dose regimen.

Results from scheduled visits will be tabulated. Unscheduled visits will be included in assessments of maximum post-baseline. All assessments will be listed.

Table 5: Populations to be used for output

Type of data	Listings	Summaries
Disposition	Screened set	Screened set
Demographic characteristics and baseline	SAF	SAF, Efficacy Analysis Set
Efficacy	SAF	Efficacy Analysis set

AE's and lab data	SAF	SAF
-------------------	-----	-----

Listings will be sorted by Study Part (i.e. B / C) and dose regimen, patient number and date/time of assessment.

Graphical presentations of the data will also be provided where appropriate.

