A visit window of ± 2 days is permitted for the Day 0 visit (the dose of radioactivity will be based on the actual administration date). Weekly assessments should occur within a window of ± 2 days. Visits occurring at 3 week intervals will have a window of ± 3 days. During the treatment and follow-up periods, a window of ± 7 days for visits is acceptable. For PET/CT and CT evaluation a window of ± 7 days is acceptable for treatment and follow-up periods.

The investigator may perform more frequent examinations than shown in Table 6-8 if clinically needed. Data from such additional examinations are also to be recorded in the eCRF.

All safety samples/assessments at baseline are to be obtained before dosing. Blood samples for haematology must be taken, analysed and evaluated within 24 hours prior to Betalutin administration.

Table 6-5 Schedule of Assessments – Part A, Phase I

Test Type	Screening	Treatment period								Follow-up period					
	Pre-study within 4 weeks before rituximab infusion	D-14 W2 prior dosing	D-1/D0 Day -1/ Dosing Day ¹² before adm	D0 Dosing Day ¹³ after adm	D1 (24±6) hours	D2 (48±12) hours	D4 (96±24) hours	D7 (168±24) hours	W 2, 3, 5, 6, 7, 9, 10, 11 Local GP (±3 days)	Month 1, 2 (±3 days)	Month 3 (±2weeks)	Month 6 (±2weeks)	Month 9 (±2 weeks)	Month 12 (±2 weeks)	W52-5 years ¹ Hospital visit every 6 months (±3 weeks)
Hospital visit	X	X	X	X	X	X	X	X		2X	X	X	X	X	8X
Informed consent	X														
Demographics	X														
Medical History	X														
Rituximab administration		X													
Lilotomab administration			X ²												
Betalutin administration				X											
Concomitant medication/therapy	X		X	X	X	X	X	X		X	X				
Cancer related treatment only excl. analgesics												X	X	X	8X
Physical examination ⁸	X		X	X ⁶	X	X	X	X		X	X	X	X	X	8X
Vital signs incl. temp	X		X	X ⁶	X	X	X	X		X	X				
Pregnancy test (if applicable)	X														
ECG			X												
WHO PS	X		X				X			X	X	X	X	X	8X
Hematology	X		X		X	X	X	X	8X	X	X	X	X	X	8X
Serum biochemistry ⁷	X		X		X	X	X	X	8X	X	X	X	X	X	8X
Lymphocyte subset	X										X	X	X	X	
Hepatitis B test	X														
Immunoglobulin levels	X										X	X	X	X	
HAMA level	X							X		X(W4 only)	X	X		X	
CD37 expression	X ³										(X ⁵)	(X ⁵)	(X ⁵)	(X ⁵)	(X ⁵)
Bone marrow biopsy	X ¹¹										X ¹⁰	X ¹⁰			
Radioactivity in blood ⁴			X	3-5X	X	X	X	X	X (week 2 and 3 only)						
Gamma Camera Images, only few pts. ⁴				X	X		X	X							
SPECT/CT ⁴							X ¹³								
Urine sampling ⁴					X										

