3.9.1 Summaries of Numeric Laboratory Results

- Study baseline and Betalutin baseline values for the following laboratory parameters: Neutrophils, Lymphocytes and Platelets.
- Only data from day 0/1 to day 92 will be included in any summary tables and plots.
- Values at each post-study baseline analysis window (scheduled visit) for all laboratory parameters.
- Change from Betalutin baseline at each post-baseline analysis window (scheduled visit) for all laboratory parameters.

A summary table will be produced for neutrophil, lymphocytes and platelet counts, by dose regimen and overall. This will include the following:

Neutrophil count

- Number (%) participants with neutrophil count $< 1 \times 10^9/L$ at any time post-Betalutin baseline (where $1 \times 10^9/L = 1\ 000/mm^3$)
- Number (%) participants with neutrophil count $< 0.5 \times 10^9/L$ at any time post-Betalutin baseline (where $0.5 \times 10^9/L = 500/mm^3$)

Platelet count will be presented in an analogous method to neutrophil count but using the following thresholds:

- platelet count $< 50 \times 10^9/L$ (where $50 \times 10^9/L = 50\ 000/mm^3$)
- platelet count $< 25 \times 10^9/L$ (where $25 \times 10^9/L = 25\ 000/mm^3$)

Lymphocyte counts will be presented in an analogous method to neutrophil count but using the following thresholds:

- Lymphocyte count $< 0.2 \times 10^9/L$ (where $0.2 \times 10^9/L = 200/mm^3$)

Mean haematological data, for each dose regimen, will be plotted for neutrophil count, platelet counts, lymphocytes, and possibly other parameters based on results. Change from baseline plots will not be produced.

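### SAP 3.4 and 3.9.1 are not reconciled on unscheduled blood counts, and the '<x' rule in SAP 3.3 can misclassify results at a cut-off; both can lower the reported severe-cytopenia rates

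*SAP*

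**What the plan says.** SAP 3.4 gives three general rules: "Results from scheduled visits will be tabulated"; "Unscheduled visits will be included in assessments of maximum post-baseline"; and "All assessments will be listed". It names neither a minimum nor a nadir.

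SAP 3.9.1 then defines a table of low counts. For neutrophils it gives the number and percentage of participants below 1 and below 0.5 × 10⁹/L, each "at any time post-Betalutin baseline". For platelets: "Platelet count will be presented in an analogous method to neutrophil count but using the following thresholds", the cut-offs being 50 and 25. Lymphocytes follow the same method with a cut-off of 0.2. All comparisons are strict. The section also sets a time limit: "Only data from day 0/1 to day 92 will be included in any summary tables and plots". Its by-visit summaries are tied to scheduled visits; the threshold counts carry no such restriction.

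SAP 3.3 deals with results recorded with an inequality sign: "then for analysis purposes a value of x will be taken".

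Protocol 6.3 lets the investigator examine patients more often than the schedule when clinically needed, and adds: "Data from such additional examinations are also to be recorded in the eCRF". Unscheduled counts can therefore be in the database.

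**The concern.** For every parameter in the 3.9.1 table the adverse direction is downwards. SAP 3.4 mentions unscheduled results only in connection with a maximum, and 3.9.1 contains no laboratory table built on a patient's highest value. The exception in 3.4 therefore does nothing for the laboratory tables and omits the case this table needs. The SAP does not say whether 3.4 or 3.9.1 prevails, so two programmers could produce different severe-cytopenia rates from the same data.

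The '<x' rule is a separate fault in the same table. A result reported as '<0.5' becomes 0.5, and 0.5 is not below 0.5, so a result known to meet the cut-off is counted as missing it.

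This matters because Protocol 4.7 names neutropenia and thrombocytopenia as the most commonly reported Grade 3/4 events. Protocol 13.4.5 planned programmatically derived CTCAE laboratory grades for the study report, but the abbreviated SAP specifies no table of them. That leaves 3.9.1 as the only laboratory-based count of severe cytopenia. The adverse event tables are a partial backstop, since Protocol 13.1.1 and 13.4.5 keep laboratory abnormalities that need no intervention or further investigation out of adverse event reporting.

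**Working it through.** The plan states no figure for this point, so there is nothing to reproduce. Three checks were made.

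**1. The '<x' rule against each strict cut-off.** With x put in place of '<x', a result is counted only if x is less than the cut-off.

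| Cut-off (× 10⁹/L) | x below cut-off | x equal to cut-off | x above cut-off |
|---|---|---|---|
| Neutrophils <1 | '<0.5' → 0.5, counted | '<1.0' → 1.0, lost | '<1.5', true status unknown |
| Neutrophils <0.5 | '<0.1' → 0.1, counted | '<0.5' → 0.5, lost | '<1.0', true status unknown |
| Platelets <50 | '<10' → 10, counted | '<50' → 50, lost | not tried |
| Platelets <25 | '<10' → 10, counted | '<25' → 25, lost | '<50', true status unknown |
| Lymphocytes <0.2 | '<0.1' → 0.1, counted | '<0.2' → 0.2, lost | '<0.5', true status unknown |

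The definite error arises only when the reporting limit equals a cut-off. The documents do not give the laboratories' reporting limits.

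**2. Scheduled counts against the nadir.** Protocol Table 6-8 gives nominal post-dose counts on Days 7, 21, 28, 35, 42, 49, 56, 63, 70, 77 and 84, with the weekly draws continuing until counts recover. The gap is 14 days from Day 7 to Day 21 and 7 days after that. Protocol 4.7 gives nadir ranges of Days 34 to 43 for platelets and Days 43 to 56 for neutrophils. Scheduled Days 35 and 42 fall in the first range, Days 49 and 56 in the second. With nominal weekly sampling, a dip of d days meets a scheduled draw with probability min(1, d/7): 3/7 = 43% for 3 days, 5/7 = 71% for 5 days, 100% for 7 days or more. Visit windows of ±2 days can stretch a weekly gap to 7 + 2 + 2 = 11 days.

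**3. Sensitivity if unscheduled counts are left out.** Inputs from Protocol Table 4-5, 40/15 regimen in Part A, n = 36: Grade 4 neutropenia in 7 (7/36 = 19.4%) and Grade 4 thrombocytopenia in 6 (6/36 = 16.7%). Let q be the share of affected patients whose only qualifying value is unscheduled; q is not in the documents and is assumed. Reported rate = true rate × (1 − q).

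| q | Neutropenia | Thrombocytopenia |
|---|---|---|
| 0 | 19.4% | 16.7% |
| 5% | 18.5% | 15.8% |
| 10% | 17.5% | 15.0% |
| 20% | 15.6% | 13.3% |

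If unscheduled counts are included, the loss from this source is zero.

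**The case against.** The strongest reply is that the specific rule already answers the general one. SAP 3.9.1 ties its by-visit summaries to scheduled visits and leaves the threshold counts open to any time after the Betalutin baseline. On its most natural reading, unscheduled counts are in. SAP 3.4 never says that unscheduled results enter the maximum alone, and its sentence on scheduled visits may describe by-visit tables only. Nor is 3.4 the SAP's only word on the matter: 3.3 includes unscheduled values in the study baseline and 3.5.2 in the last date known alive. This stands. A reader might infer that the SAP excludes unscheduled low counts and that severe cytopenia is therefore undercounted; the text supports a conflict and a risk, not that result.

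The argument also cuts the other way. Where the authors wanted unscheduled data in 3.3 and 3.5.2, they said so, and in 3.9.1 they did not. The reading remains a choice for the programmer.

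It is also fair to say that this is a descriptive, abbreviated SAP for a terminated study, that no test or dosing decision is tied to the table, that all assessments are listed with out-of-range flags (SAP 3.9), and that adverse events are tabulated by CTCAE grade (SAP Table 6). These points limit the consequence. Listings do not, however, give a rate by regimen.

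**Conclusion.** The point holds as an unreconciled pair of rules plus a definite misclassification when a reporting limit equals a cut-off. Where either error occurs, it lowers the reported rate of the main toxicity. The size is unknown. The range in the working rests on assumed values of q, on leaving unscheduled counts out, and on Part A Grade 4 rates standing in for neutrophils below 0.5 and platelets below 25.

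A reader might infer a much larger effect from Protocol 4.8.7.1. There, 4 patients had Grade 4 neutropenia and 4 had Grade 4 thrombocytopenia for more than 7 days. That leaves 7 − 4 = 3 and 6 − 4 = 2 shorter cases, and losing all of them would give 4/36 = 11.1% for each. The documents do not support that as an estimate: it assumes that scheduled draws catch none of the short episodes, and nothing says any case was seen only on an unscheduled sample. With dips of 3 to 5 days, and every missed episode found on an extra draw, the rates would be (7 − 3 × 4/7)/36 = 14.7% to (7 − 3 × 2/7)/36 = 17.1% for neutrophils, and (6 − 2 × 4/7)/36 = 13.5% to (6 − 2 × 2/7)/36 = 15.1% for platelets.

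Nor does the concern reach the duration-based dose-limiting events of Protocol 6.2.1 in any obvious way. Grade 4 toxicity that fails to improve within 7 days should meet a nominal weekly draw.

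Severity: minor, worth correcting because the remedy is nearly free.

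**What to change.** - **SAP 3.4:** replace the reference to the post-baseline maximum, so that unscheduled results enter the worst post-baseline value in the adverse direction (the minimum for blood counts) and all any-time threshold counts in 3.9.1. The existing limit to Day 92 is unaffected.
- **SAP 3.3:** add that, for threshold counts, a result reported as '<x' with x at or below the cut-off is counted as below it. A result reported as '≤x' is so counted only when x is below the cut-off, because '≤0.5' may equal 0.5 and need not meet a strict '<0.5'.

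The cost is two sentences and a small programming change. No new data are needed.

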3.5 Participant Disposition

3.5.1 Participant Enrolment

A listing of screen failed participants will be provided which will include the date of informed consent, the date of screening withdrawal, the reason for screen failing and any inclusion/exclusion criteria not met.

A listing of eligibility for participants that were recruited but did not meet all entry criteria will be provided which will include the protocol version number at the time of screening and the inclusion/exclusion criteria not met.

3.5.2 Participant Disposition

A summary of participant disposition will be provided. This summary will present number of participants applicable to each of the following:

- Screened set, including screen-failures with reason.
- SAF.
- Efficacy Analysis Set.
- Gave consent for genomic biomarker analysis of tumour tissue (listing only).
- Gave consent to HLA typing (listing only).
- Gave consent for taking part in PK assessments (listing only).
- Gave consent for taking part in dosimetry assessments (listing only).
- Participants who completed the treatment period. (was in study up to Day 92).
- Participants who discontinued during the study treatment period (up to Day 92) (with summary of reasons for withdrawal from the Completion / Withdrawal eCRF page).
- Participants who discontinued after the study treatment period (from Day 93 onwards) (with summary of reasons for withdrawal from the Completion / Withdrawal eCRF page).

The treatment period is from Day 1 to Day 92 inclusive.

All duration derivations (months) are calculated relative to the date of first Betalutin administration using the following formula:

$$\text{Time to data cut off/death/withdrawal (months)} = ([\text{date of data cut off/death/withdrawal} - \text{date of first Betalutin administration}] + 1) * 12 / 365.25$$

For all summaries except the screened summary, the denominator for the percentages of participants in each category will be the number of participants in the SAF. The denominator for the percentages of participants for the screened summaries will be the number in the screened set.

Descriptive statistics for the duration of follow-up (months) will also be included where:

$$\text{Duration of follow-up (months)} = ([\{\text{latest date participant is known to be alive}\} - \text{date of first Betalutin administration}] + 1) * 12 / 365.25 \text{ rounded to 1 decimal place.}$$

Where latest date known to be alive is obtained using all data available for the participant (i.e. eCRF (including unscheduled), response and survival follow-up data).

Completion and withdrawal data, membership of each of the analysis sets along with reasons for exclusion will be listed.

3.6 Baseline Data

3.6.1 Demographics and Baseline Characteristics

Demographic characteristics (age, sex, ethnic origin and race) and body measurements (height, weight) at screening will be summarised.

Age will be summarised as a numeric variable and by the following categories <65 and >=65. Age will be calculated in years at the date of informed consent as: *(year of informed consent – year of birth)*.

Individual participant demographic characteristics and body measurements data will be listed.

3.6.2 Medical History

Medical history events will be coded using the same Medical Dictionary for Regulatory Authorities (MedDRA) dictionary version utilised at the time of the reporting for Part A primary analysis. The version used will be indicated in the data listings. The number and percentage of subjects will be presented for ongoing conditions and previous conditions separately by system organ class (SOC), and preferred term (PT), where SOC and PT will be presented in decreasing frequency of the total number of subjects with medical history events. All events will be listed. No summary tables required for general medical history.

3.6.3 Disease History

Disease history will be reported separately for Parts B and C.

Part B:

All disease history and previous treatments for FL will be listed including any derived variables.

3.6.3.1 Initial diagnosis of Follicular Lymphoma

The following initial diagnosis information will be summarised and listed:

- Time since initial diagnosis (months): calculated as:

12[date of informed consent – date of diagnosis of FL + 1]/365.25, reported to 1 decimal place*

If partial dates are reported for date of diagnosis, the 15th will be used when day is missing and 1st July when day and month are missing.

- Subtype at initial diagnosis: grade I-IIIa or other
- Whether B symptoms were present at initial diagnosis: No, Yes or Unknown
- Transformed lymphoma in disease history (No, Yes or Unknown)

